# 16.2 Analysis of the Secondary Endpoints and Secondary Analyses of Primary Endpoints

The secondary endpoints are the following:

14-JUN-2022

Confidential & Proprietary

- Schirmer test responder event rate (≥ 10mm) measured before and after the final dose at visit 2 and 4.
- Conjunctival Redness measured outside the DEC for visit 2 and visit 4 at pre-dose and 10 minutes after doses 1, 2, and 3; and
- VAS for ocular dryness, discomfort, burning, grittiness and stinging, and ocular itching,

Statistical models and procedures that are analogous to those used for the primary efficacy analyses will be employed to evaluate secondary endpoints.

Secondary analyses of the primary endpoints will be repeated using the PP population.

#### 16.3 Multiplicity Considerations

P-values for the main effect of treatment will be ordered for the primary endpoints and Hochberg's procedure for multiplicity control will be used.

No type I error control will be utilized for exploratory endpoints. Thus, exploratory comparisons are considered hypothesis generating.

#### 17. Safety Analysis

All safety analyses will be conducted using the safety population.

An AE is defined as any untoward medical occurrence associated with the use of an IP in humans, whether or not considered IP-related. An AE can be any unfavorable and unintended sign (e.g., an abnormal laboratory finding), symptom, or disease temporally associated with the use of an IP, without any judgment about causality.

14-JUN-2022

Confidential & Proprietary

Treatment-emergent adverse events (TEAEs) are defined as any adverse event that occurs or worsens after the first dose of study treatment. AEs recorded in the eCRF which began prior to treatment will not be included in the summary tables but will be included in the AE data listings.

An overall summary will display the number of subjects who experience one or more AEs in each of the following categories:

- All TEAEs regardless of severity or presumed relationship to Study Intervention
- Treatment-Emergent AEs judged related to Study Intervention
- Treatment-Emergent Severe Adverse Events
- Treatment-Emergent Severe Adverse Events judged related to Study Intervention
- Treatment-Emergent Serious Adverse Events
- Treatment-Emergent Serious Adverse Events judged related to Study Intervention
- Treatment-Emergent Adverse Events with Fatal Outcome
- Treatment-Emergent Adverse Events with Fatal Outcome judged related to Study
  Intervention
- Treatment-Emergent Adverse Events leading to Withdrawal from the Study
- Treatment-Emergent Adverse Events leading to Withdrawal from the Study judged related to Study Intervention

The number of emergent events and the number and percentage of subjects with TEAEs will be summarized by treatment-period. SOC and PT for different categories of TEAEs. At each level of tabulation (e.g., at the PT level) subjects will be counted only once if they had more than one such event reported during the AE collection period.

The following summary tables will be presented for TEAE data:

- Treatment-Emergent Adverse Events Overview
- Treatment-Emergent Adverse Events, by Severity and Grade
- Treatment-Emergent Adverse Events, by SOC and PT
- Treatment-Emergent Severe Adverse Events, by SOC and PT
- Treatment-Emergent Serious Adverse Events, by SOC and PT
- Treatment-Emergent Adverse Events with Fatal Outcome, by SOC and PT

- Treatment-Emergent Adverse Events leading to Withdrawal from the Study, by SOC and PT
- Treatment-Emergent Drug Related Adverse Events, by SOC and PT
- Treatment-Emergent Severe Drug Related Adverse Events, by SOC and PT
- Treatment-Emergent Serious Drug Related Adverse Events, by SOC and PT
- Treatment-Emergent Drug Related Adverse Events with Fatal Outcome, by SOC and PT
- Treatment-Emergent Drug Related Adverse Events leading to Withdrawal from the Study, by SOC and PT

'Severe' will be defined as Grade 3 or above. A missing severity will be considered Grade 3.

'Drug Related' will be defined as 'Definitely Related', 'Probably related' or 'Possibly Related', excluding 'Unlikely Related' and 'Not Related'. A missing relationship will be considered as 'Definitely Related'.

Separate summaries will be provided for the following categories of AEs:

- Ocular TEAEs
- Non-ocular TEAEs

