12.3. Visit 1b: DEC Screening (Day -14 to -7)

- The subjects will be evaluated for study inclusion, exclusion and restriction criteria.
- Medical/medication will be updated for each subject.
- An SVA and SLE will be performed pre- and post-DEC ([Section 13.2.2](#) and [13.2.3](#)).
- IOP will be performed post-DEC ([Section 13.2.4](#)).
- [\[REDACTED\]](#) training will be provided to the study participants.
- Schirmer's test (baseline) will be performed prior to vehicle administration before DEC entry ([Section 13.1.2](#)).
- Vehicle will be administered in the clinic approximately 5 minutes prior to the DEC entry and 45 minutes after DEC entry.
- Subjects will be exposed to a DEC session (approximately 90 minutes)
- Staff-assessed conjunctival redness will be performed approximately -10 and -5 minutes pre-DEC entry and approximately at 10, 20, 30, 40, 55, 65, 75, 85 and 90 minutes while in the DEC ([Section 13.1.1](#) and [Table 6-2](#)). Conjunctival redness will also be performed post-DEC (1 time)
- Ocular itching score and VAS ocular symptoms (dryness, discomfort, burning, grittiness and stinging) will be assessed pre- and post-DEC.
- VAS assessments for ocular symptoms (dryness, discomfort, burning, grittiness and stinging) will be performed approximately -12 and -7 minutes prior to DEC entry (and pre-vehicle administration) and approximately at 12, 22, 32, 42, 57, 67, 77, 87 and 92 minutes while in the chamber ([Section 13.1.3](#) and [Table 6-3](#)).
- Adverse events and concomitants medications will be recorded during the visit.

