15.4.3. Safety Analysis

Safety analysis will include descriptive analysis and listings according to received treatment. Safety analysis will be performed on all subjects receiving at least one dose of study medication. Subject's safety data will be presented according to the treatment they actually received. The Safety population will be used for all analyses of safety endpoints as well as demographics and baseline characteristics.

Adverse events and Serious Adverse Events (SAE) will be classified using standard Medical Dictionary for Regulatory Activities (MedDRA) [REDACTED]

[REDACTED] Summary tables listing the type, date of onset, date and time of resolution, incidence, severity, outcome, action taken, and Investigator's opinion of relationship to the study product will be presented by treatment group for AEs reported after randomization.

Concomitant medication used during the study will be listed by treatment and subject.

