18.3.1. Recording Adverse Events

The staff will record all AEs observed, queried, or spontaneously volunteered by the subjects (regardless of seriousness or relationship to study treatment) in the appropriate section of the subject's case report form or source documents. Subjects experiencing AEs (including those withdrawn from the study due to an AE) will be followed until recovery to a satisfactory state, or stabilization, or appropriate outcome is established as judged by the Investigator. Exacerbation of conditions related to the signs and symptoms of Dry Eye will not be reported as an AE.

The following details will be recorded for AEs:

- Description of event/symptom
- Onset date and time of event
- End date and time of event

■ [REDACTED]
■ [REDACTED]
■ [REDACTED]
■ [REDACTED]
■ [REDACTED]

- Action taken with study treatment noted as follows:
 - Dose not changed
 - Dose reduced
 - Drug interrupted
 - Drug withdrawn
 - Not applicable
 - Unknown

- Any other action taken (such as concomitant medication, non-drug therapy, hospitalization or none)
- Outcome of AE noted as follows:
 - Fatal
 - Not recovered/not resolved
 - Recovered/resolved
 - Recovered/Resolved with sequelae
 - Unknown
- Causality noted as follows:

Relationship to IP: The investigator must assess whether they consider an AE to be drug-related. In assessing this relationship, the investigator must use information about the drug as outlined in the Investigator's Brochure, the subject's pre-existent medical conditions/concurrent medication, and chronology of the event relative to drug administration. The following definitions will be used:

- Definitely Related
- Probably Related
- Possibly Related
- Unlikely to be related
- Not Related

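### SAP section 17 counts AEs that worsen on treatment as treatment-emergent, then bars those that began before treatment from the summary tables

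*SAP*

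**What the plan says.** SAP section 17 gives two rules in consecutive sentences. The first defines a TEAE as "any adverse event that occurs or worsens after the first dose of study treatment". The second states that "AEs recorded in the eCRF which began prior to treatment will not be included in the summary tables". It goes on to say that these events "will not be included in the summary tables but will be included in the AE data listings", so they are kept in the listings.

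The tables concerned are TEAE tables: "The following summary tables will be presented for TEAE data" introduces the overview and the tables by severity, system organ class and preferred term, seriousness, relatedness, withdrawal and fatal outcome. Ocular and non-ocular events are also summarized separately. Counts are given by treatment-period.

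Three other places bear on the point:

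- Protocol 12.3 (Visit 1b, the chamber screening visit): "Vehicle will be administered in the clinic approximately 5 minutes prior to the DEC entry and 45 minutes after DEC entry". At that visit, "Adverse events and concomitants medications will be recorded during the visit".
- Protocol 15.4.3: the AE summary tables "will be presented by treatment group for AEs reported after randomization". It states no exclusion by onset date.
- Protocol 18.3.1: the items recorded for each AE include "Onset date and time of event" and the end date and time. The visible text does not say whether worsening opens a new AE record.

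**The concern.** For an AE that began before dosing, worsening is the only route to treatment-emergent status. The definition opens that route and the exclusion closes it. A programmer who filters on onset date would comply with the second sentence and contradict the first. Every TEAE table would inherit the filter.

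Worsening of an existing event after dosing is one of the things a TEAE table is meant to show. Where the rule has an effect on counts, it can only lower them. That also sits oddly with the rest of section 17, which treats missing data conservatively: a missing severity is taken as Grade 3, and a missing relationship as definitely related.

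**Working it through.** The documents give no figure to reproduce. The check is to apply both sentences of SAP section 17 to each kind of AE record.

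| AE record | TEAE by the definition? | Allowed in the tables by the exclusion? | Result |
|---|---|---|---|
| Began before first dose, did not worsen | No | No | Consistent |
| Began before first dose, worsened after it, one record | Yes | No | Contradiction |
| Began before first dose, worsening entered as a new record with a post-dose onset | Yes (new record) | Yes (new record) | Consistent |
| Began after first dose | Yes | Yes | Consistent |

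The conflict is confined to the second row. Whether that row is ever filled depends on how worsening is recorded, which the visible text leaves open.

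**Can such records exist?** Yes. AEs are recorded at Visit 1b, where subjects receive vehicle twice and about 90 minutes in the chamber. Visit 2, with randomization and the first randomized dose, follows 7 to 14 days later (Protocol 12.4). An AE recorded in that interval has a pre-dose onset and could persist and worsen.

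**What does treatment mean here?** Vehicle is one of the two study products (Protocol 11.1) and is already given at Visit 1b, so the phrase for events before treatment has two possible anchors. SAP 15.2 counts exposure from Visit 2 (Day 1), which points to the first randomized dose. Section 17 does not say so.

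**Size per affected subject.** Inputs: about 50 randomized subjects (SAP section 7), each planned to receive both treatments in the crossover, so about 50 subjects per treatment.

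- Largest effect of one affected subject on a tabulated incidence: 1/50 = 0.02, or 2 percentage points.
- Smallest effect: 0, either because worsening was entered as a new record or because the subject has another TEAE at the same level of the table. SAP section 17 counts a subject only once per level.

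This takes the column to be a treatment. If the columns were instead each treatment split by period, the denominator would be about 25 (SAP section 7 puts about 25 in each sequence) and the ceiling 1/25 = 4 percentage points.

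**Number of affected subjects.** Neither document gives a rate of screening-period AEs or of their worsening, so no total can be calculated.

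**The case against.** The case for leaving the text alone has real content.

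- *The events are still reported.* A reader might infer that worsened events vanish from the safety results. They do not: the same sentence keeps them in the listings. All deaths are summarized, and SAEs and AEs leading to discontinuation or withdrawal have their own listings (SAP 17.1.1 to 17.1.3). The loss is from tabulated counts and percentages.
- *The case may be rare.* A reader might infer that under-counting is likely because every randomized subject has been through the chamber at Visit 1b. Protocol 18.3.1, however, does not treat exacerbation of dry-eye signs and symptoms as an AE, which removes much of what the chamber would be expected to provoke. Eligibility is also checked again at Visit 2. The documents support possible, not likely.
- *The crossover adds no further loss of this kind.* A reader might extend the point to an AE that starts in Period 1 and worsens in Period 2. That event began after the first dose, so it is already a TEAE and stays in the tables. What the visible text lacks is a rule on which period takes the worsening.
- *A recording convention may exist elsewhere.* Parts of the AE item list in Protocol 18.3.1 are blacked out, and data handling is deferred to a Data Management Plan that is not public. If worsening always opens a new record, nothing is lost.
- *The rule is the same for both treatments.* No bias in the comparison of reproxalap with vehicle is shown.

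All of this limits the effect. None of it reconciles the two sentences: as written, they give opposite instructions for the same record, and a recording convention would make the conflict harmless without removing it from the SAP. The protocol wording does not settle the matter either, because an AE first reported before randomization and worsening later is not clearly inside or outside its scope.

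**Conclusion.** The concern holds as a contradiction between two adjacent rules in SAP section 17. Read literally, an AE that began before the first dose and worsened after it is a TEAE that appears in no TEAE summary table, only in listings and, where it applies, in the separate outputs for deaths, SAEs and discontinuations.

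The effect is bounded for each subject but unknown in total: between 0 and 2 percentage points of a tabulated incidence per affected subject, assuming about 50 subjects per treatment. Any figure for the trial as a whole would need an assumed number of affected subjects, for which the documents offer no basis; zero is possible. The contradiction itself is certain from the text. That events will actually be lost is not.

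**What to change.** Replace the exclusion sentence in SAP section 17 with: *AEs that began before the first randomized dose (Visit 2) and did not worsen after it will be listed but not summarized; AEs that began earlier and worsened after that dose are TEAEs and will be summarized under the treatment period in which they worsened.*

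This settles the anchor (Visit 2, not the Visit 1b vehicle) and the period to which such worsening belongs. Worsening should be identified from the AE data as already collected, and the SAP should say how, so no change to data collection is asked for.

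The cost is one SAP sentence with its note on identification, one programming condition, and possibly a slightly higher reported AE rate.

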# 17.1 Deaths, Serious Adverse Events and Other Significant Adverse Events

#### 17.1.1 DEATHS

All deaths occurring up to the analysis cut-off date, regardless of causality, will be summarized by cause of death.

#### 17.1.2 SERIOUS ADVERSE EVENTS

A listing of Serious Adverse Events (SAEs) occurring up to the analysis cut-off date will be provided.

SAEs occurring before study drug initiation will be listed separately.

# 17.1.3 Adverse Events Leading to Discontinuation of Study Drug or Withdrawal from Study

A listing of all AEs occurring up to the analysis cut-off date and leading to discontinuation of study drug or withdrawal from study will be presented.

#### 18. Other Safety Variables

# 18.1 Visual Acuity (ETDRS)

The Snellen Visual Acuity (SVA) will be performed pre-DEC (and pre symptom assessment) and again at post-DEC exposure. The logarithm of the minimum angle of resolution (logMAR) VA must be assessed using an ETDRS chart. The procedure used will be consistent with the recommendations provided for using the ETDRS eye chart. Subjects should use their most recent correction to attain their best-corrected visual acuity (BCVA).

The observed and change from baseline visual acuity will be summarized for OD and OS, separately. Continuous descriptive statistics by visit for each treatment condition will be presented. A subject listing of VA will also be produced.

# 18.2 Slit-Lamp Biomicroscopy Examination

A slit-lamp biomicroscopy examination of the cornea, conjunctiva, anterior chamber, iris, lens, and lid will be performed pre-DEC (and pre symptom assessment) and again at post-DEC exposure. The results will be graded as normal, Abnormal Not Clinically Significant (NCS) or Abnormal Clinically Significant (CS). Abnormal findings will be described.

The results will be summarized using counts and percentages for each treatment condition at each visit for OD and OS, separately. Percentages will be based on the number of subjects in each treatment condition with responses. Shift tables for the slit-lamp biomicroscopy parameters will also be provided comparing each follow-up visit to baseline (Visit 1b). A subject listing of the slit-lamp biomicroscopy parameters will also be produced.

#### 18.3 Intraocular Pressure (IOP)

IOP will be measured in each eye by contact tonometry by the examiner and the results will be recorded in mmHg. Intraocular Pressure (IOP) will be performed prior to DEC entry. A single measurement is made to obtain a determination of IOP. The same tonometer employing the investigator's standard technique will be used throughout the study. In addition, all reasonable efforts will be made to have the same examiner obtain all IOP measurements for a given subject.

The IOP values and changes from baseline for OD and OS, separately, will be summarized using continuous descriptive statistics by visit and eye for each treatment condition and for all actively treated subjects. A subject listing of IOP also will be produced.

#### 19. Additional Analyses

Additional analyses other than the planned analyses described herein may be conducted as ad-hoc analyses. All ad-hoc analyses will be identified in the CSR. The intent of any such analyses would be to better characterize treatment effects.

#### 20. Revision History

Documentation of revision to the SAP will commence after approval of the Final version 1.0.

#### 21. Reporting Conventions

The following reporting conventions will be adopted for the presentation of study data. These conventions will enhance the review process and help to standardize presentation with common notations.

#### 21.1 General Reporting Conventions

- All tables and data listings will be developed in Landscape Orientation, unless presented as part of the text in a CSR.
- Figures will be presented in Landscape Orientation, unless presented as part of the text in a CSR.
- Legends will be used for all figures with more than one variable or item displayed.
- Figures will be presented in color with treatment condition distinguished by different symbols and colors. Lines in figures should be wide enough to view the line after being photocopied.
- Specialized text styles, such as bolding, italics, borders, shading, superscripted and subscripted text will not be used in tables, figures, and data listings unless they add significant value to the table, figure, or data listing.
- Only standard keyboard characters should be used in tables and data listings. Special characters, such as non-printable control characters, printer specific, or font specific characters, will not be used on a table, figure, or data listing. Hexadecimal character representations are allowed (e.g.,μ,α,β).
- All titles will be centered on a page. The ICH numbering convention is to be used for all tables, figures, and data listings.
- All footnotes will be left justified and the bottom of a page. Footnotes must be present on the page where they are first referenced. Footnotes should be used sparingly and must add value to the table, figure, or data listing. If more than four footnote lines are

planned, then a cover page may be used to display footnotes.

- Missing values for both numeric and character variables will be presented as blanks in a table or data listing. A zero (0) may be used if appropriate to identify when the frequency of a variable is not observed.
- All date values will be presented as YYYY-MM-DD (e.g., 2013-05-17) ISO 8601 format.
- All observed time values will be presented using a 24-hour clock HH:MM:SS format (e.g., 01:35:45 or 11:26). Seconds should only be reported if they were measured as part of the study, also in ISO 8601 format.
- Time durations will be reported in mixed HHh MMm SSs notation (e.g., 5h 32m, or 27h 52m 31s). The use of decimal notation to present (display) time durations should be avoided (e.g., 0.083h = 5m) unless it is necessary to show the computation of time differences in a table, figure, or data listing, in which case both notations may be used to display the time duration.
- All tables, figures, and data listings will have the Table, Listing, or Figure status (DRAFT, FINAL), and a date/time stamp on the bottom of each output.
- All analysis programs developed for a table, figure, or data listing display will be selfcontained to facilitate transfer of programs to multiple computing environments and transfer to a regulatory agency (if requested).

# 21.2 Population Summary Conventions

- Population(s) represented on the tables or data listings will be clearly identified in the last title of the Table as "Population: <name of population>" and will be identical in name to that identified in the protocol or SAP.
- Consistent terminology will be used to define and identify a population.
- Sub-population(s) or special population(s) descriptions will provide sufficient detail to ensure comprehension of the population (e.g., FAS Females, Per-Protocol Males >60 years of age) used for analysis in a table or figure.
- Population sizes are presented for each treatment or dosing category as totals in the column header as (N=xxxx), where appropriate.
- Population sizes with non-missing values or subset shown with summary statistics are represented with (n) of subjects.

- All population summaries for categorical variables will include all categories that were planned and for which the subjects may have had a response. Percentages corresponding to null categories (cells) will be suppressed.
- All population summaries for continuous variables will include: N, mean, SD, minimum, and maximum. Other summaries (e.g., number missing, median, quartiles, 5%, 95% Confidence Intervals, CV or %CV) may be used as appropriate.
- All percentages are rounded and reported to xx.x%. A percentage of 100% will be reported as 100%. No value of 0% will be reported. Any computation of percent that results in 0% is to be presented as a blank.
- Population summaries that include p-values will report the p-value to four decimal places with a leading zero (0.0001). All p-values reported on default output from statistical software (i.e., SAS® Software version) may be reported at the default level of precision. P-values <0.0001 should be reported as <0.0001 not 0.0000.

